9.4.5 Alzheimer's Disease Composite Score (ADCOMS)

The Alzheimer's Disease Composite Score³ is a function of components of the ADAS-Cog, MMSE and CDR-SB, and ranges from 0 to 1.97. It is calculated by weighting the score for each of the following by the coefficient, and taking the sum:

Table 2. Derivation of ADCOMS

		PLS coefficient
ADAS-Cog	Delayed word recall	0.008
	Orientation	0.017
	Word recognition	0.004
	Word finding difficulty	0.016
MMSE	Orientation time	0.042
	Drawing	0.038
CDR-SB	Personal care	0.054
	Community affairs	0.109
	Home and hobbies	0.089
	Judgment and problem solving	0.069
	Memory	0.059
	Orientation	0.078

[figure not shown]
The change from baseline in the ADCOMS score will be analyzed at Week 12 using an ANCOVA including treatment group and the randomization stratum as main effects and the baseline ADCOMS score as a covariate.

The effect size for each treatment group will be provided.

9.5 Efficacy Subgroup Analyses

The primary endpoint will be conducted for the following subsets of participants. Within each subgroup category, data will be divided into mutually exclusive subsets and then a separate analysis will be performed for each subset (e.g., for the "Sex" category, a separate analysis will be performed for all male participants and the same analysis will be performed for all female participants.)

- On symptomatic treatment for AD at baseline: Yes, No
- Sex
- Age: < 65 years or ≥ 65 years and < 75 years or ≥ 75 years

Other subgroup analyses (e.g., subgroups based on biomarkers) may be conducted given sufficient data.

The MMRM will include treatment group, visit, treatment-by-visit interaction, and the randomization stratum (for the age and sex subgroups only) as fixed effects and the baseline ADAS-Cog 14 score as a covariate. The unstructured covariance structure will be used to estimate the within-participant variance-covariance. Denominator degrees of freedom will be computed using the Kenward-Roger method. The group mean treatment difference between each dose and placebo at Week 12 will be based on contrasts from this model. If the model fails to converge with an unstructured covariance structure, the compound symmetry covariance structure will be substituted. If the model still fails to converge, descriptive statistics based on the univariate summaries will be provided.

[figure not shown]

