5.8 Randomization/Drug Assignment

All participants will be assigned a unique identification number by the IRT system at Screening Visit 1. For participants who rescreen, the screening number assigned by the IRT system should be used throughout the study. The IRT will assign the participant to a treatment group at Baseline/Day 1 according to the randomization schedule.

Randomization will be in a 1:1:1:1 ratio to placebo, ABBV-552 1 mg QD, ABBV-552 5 mg QD, or ABBV-552 15 mg QD.

Participants will be stratified, based on whether they are currently not taking symptomatic treatment for AD vs. those who are receiving a stable dose of symptomatic treatment for AD, at Baseline/Day 1.

Each stratum should contain approximately 40% to 60% of all randomized participants.

All AbbVie personnel with direct oversight of the conduct and management of the trial (with the exception of AbbVie Drug Supply Management Team), the investigator, study site personnel, and the participant will remain blinded to each participant's treatment throughout the study. To maintain the blind, the ABBV-552 tablets and placebo tablets provided for the study will be identical in appearance. The IRT will provide access to unblinded participant treatment information in the case of a medical emergency.

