7.4 Statistical Analyses for Efficacy

Analysis of the primary and all other efficacy endpoints will be conducted on the mITT analysis set based on 2-sided α = 0.1 level, unless otherwise specified in the SAP.

Summary and Analysis of the Primary Endpoint

The primary analysis of ADAS-Cog 14 will be conducted using an MMRM including treatment group, visit, treatment-by-visit interaction, and the randomization stratum as fixed effects and the baseline ADAS-

Cog 14 score as a covariate. The unstructured covariance structure will be used to estimate the within participant variance-covariance. Denominator degrees of freedom will be computed using the Kenward-Roger method. The group mean treatment difference between each dose and placebo at Week 12 will be based on contrasts from this model.

Summary and Analysis of Additional Efficacy Endpoint

The following analyses will generally apply unless otherwise noted in the SAP. For continuous efficacy endpoints, the mean, standard deviation, median, minimum, and maximum will be reported for each treatment group. For endpoints measured at a single post-baseline time point, the between-group treatment summary will be based on an analysis of covariance (ANCOVA) including treatment group, randomization stratum, and baseline for that respective parameter. For endpoints measured at multiple post-baseline time points, the between-group treatment summary at each visit will be conducted using an MMRM including treatment group, visit, treatment-by-visit interaction, and the randomization stratum as fixed effects and the baseline values associated with the endpoint as a covariate. Missing data will not be imputed before performing the MMRM.

Subgroup Analysis for Efficacy

Subgroup analyses of the primary endpoint will be conducted for the following subgroups.

- On symptomatic treatment for AD at baseline: Yes, No
- Sex
- Age: < 65 years or ≥ 65 years and < 75 years or ≥ 75 years

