7.8 Sample Size Determination

It is assumed that the treatment difference of ADAS-Cog 14 score change from Baseline at Week 12 between ABBV-552 and placebo is 2.85 with a pooled standard deviation of 5.7. Assuming a 20% discontinuation rate, 60 participants randomized per group will provide about 80% power to detect the above treatment difference in ADAS-Cog 14 score at the 2-sided 10% significance level.

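### The subgroup analyses fit a separate model in each subset and never estimate the difference in treatment effect between subsets

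*SAP*

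**What the plan says.** Protocol 7.4 states that "Subgroup analyses of the primary endpoint will be conducted for the following subgroups", then lists symptomatic AD treatment at baseline (yes/no), sex and three age bands. It gives no method for them.

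SAP 9.5 supplies the method: "data will be divided into mutually exclusive subsets and then a separate analysis will be performed for each subset". Each MMRM has treatment, visit, treatment-by-visit and baseline ADAS-Cog 14. The randomization stratum is included for the age and sex subsets only. The output is described as follows: "The group mean treatment difference between each dose and placebo at Week 12 will be based on contrasts from this model". SAP 9.5 also leaves room for further subgroups, for example by biomarker.

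No treatment-by-subgroup term appears in SAP 9.5. The primary MMRM in SAP 9.3.2 carries the stratum as a main effect only, and SAP 11.0 says that every planned analysis has already been listed.

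On the size of the strata, Protocol 5.8 says: "Each stratum should contain approximately 40% to 60% of all randomized participants".

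**The concern.** A subgroup analysis asks whether the treatment effect differs between levels of a factor. The quantity that answers it is the between-level difference in effect, with its uncertainty. The plan produces the within-level effects and stops there.

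A reader given two within-stratum results will compare them, by which one is significant or by how far apart the point estimates lie. Both comparisons are unreliable when each stratum holds about half of a trial sized for about 80% power overall. The on/off symptomatic-treatment split is the natural place for this to happen: it is the randomization factor, both strata will be sizeable, and SAP 10.6 repeats the split for safety. Chance could then be taken for a real difference between participants on and off symptomatic treatment, and biomarker subgroups added under SAP 9.5 could be read in the same way.

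**Working it through.** **Inputs.** Protocol 7.8: the assumed difference "between ABBV-552 and placebo is 2.85 with a pooled standard deviation of 5.7", tested "at the 2-sided 10% significance level" (critical value 1.645). Also Protocol 7.8: "Assuming a 20% discontinuation rate, 60 participants randomized per group will provide about 80% power". That gives 60 × 0.8 = 48 evaluable per arm. Protocol 5.8: "Randomization will be in a 1:1:1:1 ratio to placebo" and the three doses, so the doses share a placebo arm; each stratum holds 40% to 60%, or about 19 to 29 evaluable per arm, and 24 at an even split.

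**Assumptions added here.** SD 5.7 in both strata, loss equal across arms and strata, no precision gain from baseline or Week 6 data, and an effect that is *identical* in the two strata.

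**The plan's own figure.** SE = 5.7 × √(2/48) = 1.164; power = Φ(2.85/1.164 − 1.645) = 78.9% (78.4% by noncentral t). This agrees with the stated figure of about 80%.

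**Power within one stratum.** Even split: SE = 5.7 × √(2/24) = 1.645; power = Φ(2.85/1.645 − 1.645) = 53.5% (52.5% by t). A 40/60 split gives 46.2% and 60.0%.

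**Significant in exactly one stratum, per dose.** The strata are independent, so the probability is p₁(1 − p₂) + p₂(1 − p₁).
- Even split: 2 × 0.535 × 0.465 = 49.8% (both strata 28.6%, neither 21.6%).
- 40/60 split: 0.462 × 0.400 + 0.600 × 0.538 = 50.8%.
- All 60 per arm evaluable: 47.4% (even) or 48.7% (40/60).

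The figure depends on the true effect (even split, 24 per arm per stratum):

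| True effect, both strata | Power per stratum | Exactly one stratum |
|---|---|---|
| 1.0 | 15.0% | 25.5% |
| 2.0 | 33.4% | 44.5% |
| 2.85 | 53.5% | 49.8% |
| 4.0 | 78.4% | 33.9% |

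**Across the three doses.** Simulation with a shared placebo arm in each stratum, 400,000 trials:
- All three doses at 2.85: at least one dose is significant in exactly one stratum in 83% of trials (84% at 40/60).
- Only one dose works: 58% if significance counts only in favour of the drug, 65% if it counts in either direction.

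**Gap in point estimates, no p-value used.** SE of the gap = 5.7 × √(4/24) = 2.327. P(|gap| ≥ 2.85) = 2 × [1 − Φ(2.85/2.327)] = 2 × [1 − Φ(1.225)] = 22% per dose, and 47% for at least one of three doses by simulation. At 40/60 the per-dose figure is 23%.

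**What a direct contrast would give.** SE 2.33; 90% CI half-width 1.645 × 2.327 = 3.83 points. Equal effects are flagged as different 10% of the time per dose at the two-sided 10% level. Power is Φ(1.225 − 1.645) = 34% for a true difference of 2.85 points and 79% for one of 5.7 points.

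**The case against.** Much of the case on the other side stands.

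- SAP 9.5 states no rule for declaring a subgroup effect and does not call for subgroup p-values, whereas SAP 9.3.2 asks for a p-value explicitly. SAP 9.1 applies the 0.1 level only where testing is specified. The significance-based figures therefore describe how readers may behave, not a planned decision.
- Both documents call the study hypothesis-generating and waive Type I error control. That is fair, but the request here is for an estimate with an interval, which a hypothesis-generating study needs.
- The subsets do not overlap, so a reader with both estimates and SEs can work out the gap and its SE. True for a two-level factor. It is still better reported than left to the reader.
- The design effect puts per-stratum power close to 50%, where the one-stratum-only pattern is most frequent. The table above shows the fall on either side.

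Three stronger readings are tempting and are not supported:

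- A reader might infer that equal effects will usually make the drug appear to work in one stratum only. For a given dose it is about a coin toss at the design effect. For the drug as a whole (some dose significant in one stratum, none in the other) it is 34% to 36% when all three doses work and about 50% when one does. The 83% is a different statement: at least one dose shows the pattern.
- A reader might infer that a choice between monotherapy and add-on use rests on these results. No passage says so; the 40% to 60% range in Protocol 5.8 is an enrolment target.
- A reader might infer a material loss of precision in the small age bands. The documents give no age distribution from which to size it.

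**Conclusion.** The gap is real: SAP 9.5 yields within-subset effects only, and neither document plans an estimate of the difference between subsets. With identical true effects of 2.85 points in both AD-treatment strata, a given dose is significant in exactly one stratum about 50% of the time, falling to about 26% at 1.0 point and 34% at 4.0. At least one dose shows the pattern in about 83% of trials if all three are equally effective, and in about 58% to 65% if one works. A gap as large as the whole design effect arises by chance 22% of the time per dose.

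These figures rest on a common SD of 5.7, 20% loss spread evenly, and no covariate gain. The significance-based ones also assume that readers judge each subset at the 10% level. The consequence is a risk of misreading exploratory results. The primary estimate and test are not affected.

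**What to change.** For each factor, replace the split fits in SAP 9.5 with one MMRM on the full mITT set: the primary model's terms plus subgroup, subgroup-by-visit, treatment-by-subgroup and treatment-by-subgroup-by-visit. For symptomatic AD treatment, the stratum term already in the model is the subgroup main effect and should not be entered again.

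From that model, report each dose-minus-placebo difference at Week 12 within each level, and the between-level difference in effect for each dose with a 90% CI. Use the same model for any biomarker subgroup added later.

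Add two statements: subgroup differences are read from the between-level contrast and not from per-subset p-values; and the contrast is imprecise (for the AD-treatment strata, SE about 2.33 points, 90% CI about ±3.8, about 34% power for a 2.85-point difference), so a null result does not show homogeneity.

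The cost is SAP wording and one model per factor in place of two or three. Data collection, sample size and the primary analysis do not change. The small downside is that a common covariance is assumed across subgroup levels, which separate fits avoid.

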10.0 Safety Analyses

10.1 General Considerations

Safety data will be summarized for the Safety Analysis Set. Safety summaries will be presented by treatment group, including a total group for all participants on active study treatment (ABBV-552 1 mg, 5 mg, 15 mg) unless otherwise noted.

10.2 Adverse Events

Adverse events (AEs) will be summarized and presented using primary MedDRA System Organ Classes (SOCs) and preferred terms (PTs) according to the version of the MedDRA coding dictionary used for the study at the time of final database lock. The actual version of the MedDRA coding dictionary used will be noted in the AE tables and in the clinical study report. Specific adverse events will be counted once for each Participant for calculating percentages, unless stated otherwise. In addition, if the same adverse event occurs multiple times within a Participant, the highest severity and level of relationship to investigational product will be reported.

10.2.1 Treatment-Emergent Adverse Events

Treatment-emergent adverse events (TEAEs) are defined as any AE with an onset date that is after the first dose of study treatment and no more than 30 days after the last dose of study treatment. Events where the onset date is the same as the study treatment start date are assumed to be treatment-emergent. All treatment-emergent AEs will be summarized overall, as well as by primary MedDRA SOC and Preferred Term. The SOCs will be presented in alphabetical order, and the PTs will be presented in alphabetical order within each SOC.

The number and percentage of participants experiencing treatment-emergent AEs will be summarized.

[figure not shown]

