Such an event can result from use of the drug as stipulated in the protocol or labeling, as well as from "special situations" such as accidental or intentional overdose, medication error, occupational or accidental exposure, off-label use, drug abuse, drug misuse, or drug withdrawal, all which must be reported whether associated with an AE or not. Any worsening of a pre-existing condition or illness is considered an AE. Worsening in severity of a reported AE should be reported as a new AE. Laboratory abnormalities and changes in vital signs are considered to be AEs only if they result in discontinuation from the study, necessitate therapeutic medical intervention, and/or if the investigator considers them to be AEs.

The investigators will monitor each participant for clinical and laboratory evidence of AEs on a routine basis throughout the study. All AEs will be followed to a satisfactory conclusion.

An elective surgery/procedure that occurs during a study will not be considered an AE if the surgery/procedure is being performed for a pre-existing condition. However, if the pre-existing condition deteriorates unexpectedly during the study (e.g., surgery performed earlier than planned), then the deterioration of the condition for which the elective surgery/procedure is being done will be considered an AE.

If an AE, whether associated with study drug or not, meets any of the following criteria, it is to be reported to AbbVie clinical pharmacovigilance as a SAE within 24 hours of the site being made aware of the SAE (refer to Section 4.2 of the Operations Manual for reporting details and contact information):

Death of Participant An event that results in the death of a participant.

Life-Threatening An event that, in the opinion of the investigator, would have

resulted in immediate fatality if medical intervention had not been taken. This does not include an event that would have been fatal if it

had occurred in a more severe form.

Hospitalization or Prolongation of Hospitalization An event that results in an admission to the hospital for any length of time or prolongs the participant's hospital stay. This does not include an emergency room visit or admission to an outpatient

facility.

Congenital Anomaly An anomaly detected at or after birth, or any anomaly that results in

fetal loss.

Persistent or Significant Disability/Incapacity

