An event that results in a condition that substantially interferes with the activities of daily living of a study participant. Disability is not intended to include experiences of relatively minor medical significance such as headache, nausea, vomiting, diarrhea, influenza,

and accidental trauma (e.g., sprained ankle).

Important Medical Event Requiring Medical or Surgical Intervention to Prevent Serious Outcome An important medical event that may not be immediately life-threatening or result in death or hospitalization, but based on medical judgment may jeopardize the participant and may require medical or surgical intervention to prevent any of the outcomes listed above (i.e., death of participant, life threatening, hospitalization, prolongation of hospitalization, congenital anomaly, or persistent or significant disability/incapacity). Additionally, any elective or spontaneous abortion or stillbirth is considered an important medical event. Examples of such events include allergic bronchospasm requiring intensive treatment in an emergency room or at home, blood dyscrasias or convulsions that do not result in inpatient hospitalization, or the development of drug dependency or drug abuse.

All adverse events reported from the time of study drug administration until 30 days after discontinuation of study drug administration will be collected, whether solicited or spontaneously reported by the participant. In addition, study procedure-related serious and nonserious adverse events will be collected from the time the participant signs the study-specific informed consent.

The following definitions will be used for Serious Adverse Reactions (SAR) and Suspected Unexpected Serious Adverse Reaction (SUSAR):

SAR Defined as all noxious and unintended responses to an investigational medicinal

product (IMP) related to any dose administered that result in an SAE as defined

above.

SUSAR Refers to individual SAE case reports from clinical trials where a causal

relationship between the SAE and the IMP was suspected by either the sponsor or the investigator, is unexpected (not listed in the applicable Reference Safety

Information), and meets one of the above serious criteria.

AbbVie will be responsible for SUSAR reporting for the IMP in accordance with global and local requirements.

Adverse events will be monitored throughout the study to identify any of special interest that may indicate a trend or risk to participants.

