7.5 Statistical Analyses for Safety

General Considerations

Safety analyses will be carried out using the safety analysis set. Safety will be assessed by AEs, lab values, vital sign measurements, ECG, and C-SSRS. For continuous safety outcomes, the change from Baseline will be analyzed in a descriptive manner by treatment group and by visit. For categorical safety outcomes, the number and percentage of participants in each category will be summarized by treatment group and by visit. Shift of laboratory values from Baseline to defined time points will be tabulated. Hypothesis testing will not be performed for safety parameters.

Analysis of Adverse Events

All AEs will be coded using the current version of the Medical Dictionary for Regulatory Activities (MedDRA). The number and percentage of participants with TEAEs, treatment-emergent SAEs, AEs with a reasonable possibility of being related to study drug, and AEs leading to study drug discontinuation will be summarized by treatment group and will be tabulated using primary MedDRA system organ class (SOC) and preferred term (PT). Treatment-emergent AEs will be defined as all events that begin or worsen (increased in intensity or became serious) on or after first dose of study drug. An AE occurs more than 30 days after the last dose will not be counted as a TEAE.

Analysis of Laboratory Data

Changes from Baseline in continuous laboratory parameters will be summarized by n, mean, standard deviation, minimum value, median, and maximum value for each treatment group and all participants overall for each continuous hematology, chemistry, and urinalysis variable.

Laboratory observations will be categorized according to CTCAE Version 4.0 and higher. For each hematology, chemistry, and urinalysis with a reference range, shift tables will be prepared for shifts from baseline to highest post-baseline grade and shifts from Baseline to the final value during the entire study for each treatment group.

Analysis of Vital Signs

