10.2.3 Treatment-Emergent Adverse Events by SOC and/or PT

Treatment-emergent adverse events will be summarized by SOC and PT; by maximum relationship to study treatment as assessed by the investigator (e.g., reasonable possibility or no reasonable possibility) and SOC and PT; by maximum grade and SOC and PT; and

by Participant number and SOC and PT. Specific adverse events will be counted once for each Participant for calculating percentages, unless stated otherwise. In addition, if the same adverse event occurs multiple times within a Participant, the highest severity and level of relationship to investigational product will be reported.

In addition, treatment-emergent adverse events will be summarized by PT and sorted by decreasing frequency for the total active group.

10.2.4 Deaths, Serious Adverse Events, and Adverse Events Leading to Study Treatment Discontinuation

Treatment-emergent serious adverse events (SAEs), TEAEs leading to premature discontinuation of study treatment, and TEAEs leading to death will be summarized by SOC and PT.

Tabular listings will be provided for all deaths, TESAEs, and TEAEs leading to premature discontinuation of study treatment.

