14.1 Changes to Planned Analyses in the Protocol

There are currently no changes to the planned analyses in the protocol.

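### SAP 10.2.1 defines TEAEs by onset date alone and omits, without declaring it, the protocol's limb for events that worsen or become serious on drug, so a narrow class of SAEs can be missing from the final SAE outputs

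*SAP*

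**What the plan says.** Protocol 7.5 defines treatment-emergent events as "all events that begin or worsen (increased in intensity or became serious) on or after first dose of study drug". It stops counting 30 days after the last dose.

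SAP 10.2.1 reads: "Treatment-emergent adverse events (TEAEs) are defined as any AE with an onset date that is after the first dose of study treatment". It also stops counting 30 days after the last dose. Its next sentence settles the boundary day: "Events where the onset date is the same as the study treatment start date are assumed to be treatment-emergent". Neither sentence mentions worsening or seriousness.

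SAP 1.0 says the SAP contains changes from the protocol's analyses and points to 14.1 for them. Section 14.1 states: "There are currently no changes to the planned analyses in the protocol".

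Two rules in protocol 6.1 bear on the consequence. On events before dosing: "study procedure-related serious and nonserious adverse events will be collected from the time the participant signs the study-specific informed consent". On worsening: "Worsening in severity of a reported AE should be reported as a new AE".

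In the final analysis, the serious-event row of the AE overview (SAP 10.2.2) and the SAE table by SOC and PT (SAP 10.2.4) are both restricted to treatment-emergent events. On listings, SAP 10.2.4 says: "Tabular listings will be provided for all deaths, TESAEs, and TEAEs leading to premature discontinuation of study treatment".

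**The concern.** The two documents give different definitions of the quantity that drives almost every AE table, and the section meant to record such differences says there are none. A programmer working from the SAP will use onset date alone.

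Severity and seriousness are separate attributes in this protocol. Severity is a CTCAE grade. Seriousness depends on outcome: death, threat to life, hospital admission, disability and so on. Protocol 7.5 names the two as separate ways to worsen. A rule that re-dates an event when its grade rises does not, on its face, re-date it when only its seriousness changes.

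At stake is the completeness of the SAE count by arm in a study with about 60 participants per arm.

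**Working it through.** No figure in the plan has to be reproduced here. The check compares the definitions and then traces where each kind of event would appear.

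**Definitions side by side**

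| Element | Protocol 7.5 | SAP 10.2.1 |
|---|---|---|
| Begins on or after first dose | counted | counted, same-day onset included |
| Intensity rises on or after first dose | counted | not mentioned |
| Becomes serious on or after first dose | counted | not mentioned |
| Upper limit | 30 days after last dose | 30 days after last dose |

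**Can a collected AE have onset before the first-dose date?** Yes, if it is related to a study procedure, since those are collected from consent. The activity schedule has AE assessment at both screening visits and at Baseline. Screening Visit 2 is at least 7 days after Visit 1, and Baseline at least 7 days after Visit 2, so the pre-dose period is at least 7 + 7 = 14 days. The documents show that such events would be collected, not that any occurred.

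**Trace through the final outputs**

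1. *Onset on the first-dose date, serious.* Treatment-emergent under both documents. Captured.
2. *A pre-existing condition worsens on drug.* Protocol 6.1 makes the worsening itself an AE, which would have its onset on drug. Captured.
3. *Pre-dose AE whose grade rises on drug and which becomes serious.* Protocol 6.1 requires a new AE record, hence an on-drug onset. Captured.
4. *Pre-dose AE that becomes serious on drug with no new record, not fatal.* Treatment-emergent under protocol 7.5, but not under SAP 10.2.1. Missing from the serious-TEAE row, the SAE table and the SAE listing.
5. *As 4, but fatal.* Missing from the SAE table and from the table of TEAEs leading to death. Present in the all-deaths count (SAP 10.2.2) and the deaths listing (SAP 10.2.4), neither of which is limited to treatment-emergent events.
6. *SAE that begins and ends before dosing.* Not treatment-emergent under either document, so not part of this discrepancy.

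Case 4 is lost outright, and case 5 in part. SAP 11.0 says that all planned analyses are in the preceding sections, so no further SAE listing appears elsewhere in the SAP.

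**Size of one missed event**

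One participant in an arm of 60: 1 / 60 = 0.0167, or 1.7 percentage points. In the pooled active group of 3 × 60 = 180: 1 / 180 = 0.0056, or 0.6 percentage points. The documents give neither a rate of procedure-related AEs during screening nor a rate at which they become serious, so no expected number is offered.

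**The case against.** A reader might infer that every AE which began before dosing and turned serious on drug is absent from all SAE outputs. The documents do not support that. Protocol 6.1 brings back events whose severity rises, SAP 10.2.1 itself counts same-day onset, and all deaths are counted and listed. The interim SAE table in SAP 12.0 is worded without the treatment-emergent restriction, so it might show some of these events. Same-day onset matters because the Baseline procedures take place on the day of the first dose.

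A reader might also infer that SAEs confined to screening are wrongly left out. Protocol 7.5 itself plans to summarise treatment-emergent SAEs, so the SAP follows the protocol there. Listing every SAE from consent would be an extension of the plan, not a correction.

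The strongest remaining objection is that the gap may already be closed in a text not available here. Protocol 6.1 refers to Operations Manual Section 4.2 for SAE reporting details, and only the title of that appendix is available. If it tells sites to open a new record when an event becomes serious, case 4 would gain an on-drug onset. It is also reasonable to expect that many events leading to hospital admission would be graded higher at the same time and so fall under case 3.

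These points make the affected class small. They do not remove the mismatch between the two definitions or the statement in SAP 14.1 that there is none.

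**Conclusion.** SAP 10.2.1 is wrong as written: it narrows the protocol's TEAE definition and does not declare the change. The practical gap is limited to a non-fatal, procedure-related AE with onset before the first-dose date that becomes serious on drug without a new AE record. The protocol counts that event; the SAP's final SAE row, table and listing do not.

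This rests on two assumptions: that sites follow the new-record rule for a rise in severity, and that no equivalent rule for seriousness exists in the Operations Manual. If the second fails, only the undeclared difference in wording remains.

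Such events should be rare. One would move an arm of 60 by 1.7 percentage points. Efficacy results are unaffected. This is a minor point, worth correcting because it concerns SAE counts and costs little.

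**What to change.** In SAP 10.2.1, restore the protocol's definition: an AE is treatment-emergent if it begins, rises in intensity or becomes serious on or after the first dose and within 30 days of the last dose. Add that an event which becomes serious is classified by the date it first met a seriousness criterion, not by its original onset date. With that change the overview row, SAE table and SAE listing pick up the event without further edits.

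If the Operations Manual already requires a new record when seriousness changes, the SAP should say so. Declaring the onset-only rule in SAP 14.1 would make the difference visible but would leave case 4 uncounted.

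The cost is about two sentences in the SAP, a small programming change and possibly a slightly higher SAE count. The sponsor should first confirm that the date an event became serious is captured, because the text available does not show whether the eCRF holds it.
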